We propose a 2-year study to examine how infant egg consumption (age of introduction and frequency of intake) influences physical growth, obesity, cardio-metabolic health, risk of food allergy, and cognition development in mid-childhood and adolescence. We will use existing data from two US longitudinal birth cohorts that tracked mother-child dyads from pregnancy to adolescence: 1) Project Viva (1999-present) that enrolled 2,341 pregnancies and followed children at delivery, 6 months (m), then yearly from 1 year (y) to 15 y of child age, and 2) the Infant Feeding Practices Study II (IFPS II, 2005-2007) that enrolled 3,033 pregnancies with surveys in late pregnancy, neonatal (1 m), then monthly from 2 m to 12 m of infant age, and at 6 y. For **Aim 1**, we will classify infants based on their age of egg introduction: never, <2 m, 2-3 m, 4-5 m, 6-8 m, 9-11 m, and ≥ 12 m. We will compare physical growth, obesity, cardio-metabolic health, food allergy, and cognition test scores in mid-childhood and adolescence. We will fit multivariable linear or logistic regression models with fractional polynomial functions of infant age of egg introduction. Both linear (e.g., earlier introduction, higher probability of the outcome) and non-linear (e.g., threshold effect) associations will be tested. For **Aim 2**, we will classify infants based on their frequency of egg intake: never, <once/week, once/week, 2-4 times/week, nearly daily or daily, and ≥ 2 times/day. We will use similar analytic methods mentioned above to compare their later outcomes. Finally, we will create an average probability of multiple child outcomes to balance across different aspects of child health and development. We will identify the lowest-risk infant egg consumption when the corresponding average predicted probability of the related adverse outcomes is the lowest.

Section 2: Detailed Research Plan

1) Background Information:

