Hypotheses: The effects of infant age of egg introduction and frequency of egg intake will vary by the child outcome of interest (**Hypothesis 1**). We predict a non-linear association between age of egg introduction and the average probability of multiple child outcomes (i.e., stunting, underweight, obesity, high risk of metabolic syndrome, food allergy, and cognitive delay), with the optimal age being a time point that falls between 6-12 months (**Hypothesis 2**). We also predict a non-linear association between frequency of infant egg intake and the average probability of multiple child outcomes, with the optimal frequency being 2-4 times per week (**Hypothesis 3**).

3) Project Design:

Sample/Data. We propose a 2-year study to examine the extent to which two important aspects of infant egg consumption (i.e., age of introduction and frequency of intake) influence physical growth, obesity, cardio-metabolic health, risk of food allergy, and cognition development in mid-childhood and adolescence. Guided by a life course framework (**Figure 1**), we will use existing secondary data from two US longitudinal birth cohorts that tracked mother-child dyads from pregnancy to adolescence: 1) **Project Viva** (1999-present, N=2,128 newborns) that followed children at delivery, 6 months (m), 1 year (y), 2 y, 3 y, 4 y, 5 y, 6 y, 7 y, 8 y, 9 y, 10 y, 11 y, 12-13 y, 14 y, and 15 y of child age,³⁷ and 2) **Infant Feeding Practices Study II** (IFPS II, 2005-2012, N=3,033 newborns) that followed children at neonatal (1 m), 2 m, 3 m, 4 m, 5 m, 6 m, 7 m, 9 m, 10 m, 12 m, and 6 y of child age.^{38,39} The PI has access to both datasets, and has 3 publications on infant nutrition, early childhood diet, growth, and obesity using Project Viva^{40,41} and IFPS II⁴² data since 2014. These two studies have a similar study design and complementary measures of child outcomes, which provide a unique opportunity for comprehensive analysis on the health effects of infant egg consumption and also external replication of findings.

Exposure measures (infant egg consumption). We will focus on age of introduction and frequency of intake as the key exposure measures of infant egg consumption, because evidence

Infant Egg Consumption | Child Health and Cognition | Clinical Guidelines

Figure 1. Conceptual framework on effects of infant egg consumption

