For **Aim 1 (infant age of egg introduction)**, we will first classify the infants based on their age of egg introduction: never, <2 m, 2-3 m, 4-5 m, 6-8 m, 9-11 m, and 12 m. Then we will compare their physical growth, obesity, cardio-metabolic risk profile, risk of food allergy, and cognition test scores in mid-childhood and adolescence using Chi-square tests (categorical outcomes) or ANOVA tests (continuous outcomes). We will fit multivariable linear (continuous outcomes) or logistic (binary outcomes) regression models with fractional polynomial functions of infant age of egg introduction, adjusted for significant confounders. Both linear (e.g., earlier introduction, high probability of the outcome) and non-linear (e.g., threshold effect) associations will be tested. The non-linear trend will be examined through visualization of scatter plots and statistical tests of polynomial term of infant age of egg introduction in the regression models. If the polynomial terms of age are not significant, we will drop it and consider the association to be linear.

Then, we will fit a mixed effect model (SAS PROC MIXED) for continuous outcomes (height z-score and BMI z-score) and a generalized linear mixed effect model (SAS PROC GLIMMIX) for binary outcomes (obesity and diagnosis of food allergy) that were measured repeatedly across multiple age points. The mixed effect model will include random intercepts, random slopes for age effects, and autoregressive variance-covariance matrix across different time points. Independent variables in the model will include infant age of egg introduction, outcome age point (mid-childhood and adolescence), the 2-way interaction term (infant age of

egg introduction × outcome age point), and significant covariates. The 2-way interaction term quantifies the extent to which infant age of egg introduction can affect the specific outcome. The PI has experience with using mixed effect models for examine child growth measures and multiple publications in this area.^{51,52}

For **Aim 2 (frequency of infant egg intake)**, we will first classify the infants based on their frequency of egg intake: never, <once/week, once/week, 2–4 times/week, nearly daily or daily, and ≥ 2 times/day. Then, we will use similar analytic methods mentioned above for Aim 1 to compare their health and developmental outcomes.

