In addition, we will create an **average probability of multiple child outcomes** to balance across different aspects of child health and development using the methods published by Oken et al.⁵³ for identifying the lowest-risk exposure level when multiple outcomes are considered. Specifically, we will focus on 6 binary child outcomes including stunting, underweight, obesity, high risk of metabolic syndrome (e.g., z score $\geq 95^{\text{th}}$ percentile), food allergy, and cognitive delay (e.g., standardized cognition score < 85 points). We will use estimates from aforementioned logistic models to generate predicted probabilities of each of the 6 adverse outcomes when the independent variable of infant egg consumption (i.e., age of egg introduction or frequency of egg intake) varies across the observed range within our study sample. We will calculate the average probability of the 6 outcomes, assuming these outcomes are equally important. We will identify the lowest-risk infant egg consumption when the corresponding average probability of the 6 adverse outcomes is the lowest.

We will handle missing data with Multiple Imputation.⁵⁴ Specifically, we will first generate 20 replicates of datasets (PROC MI in SAS) with imputed values for missing data on infant egg consumption, child outcomes, and significant covariates, based on a bayesian approach. The 2nd stage is to use standard statistical methods (e.g., Linear Regression) to fit the model of interest to examine the association between infant egg consumption and the specific outcome within each of the 20 imputed datasets. The 3rd stage is to pool the analytic results from all 20 imputed datasets to get the average estimates of the association (PROC MIANALYZE). The PI has experience with Multiple Imputation for large datasets.⁵⁵

All our analyses will be first conducted among boys and girls separately to examine the potential sex differences. A formal interaction test will be conducted by including the interaction term of egg consumption and sex into the regression models. If the interaction term is significant, sex-stratified results will be reported. Otherwise, sex-pooled analytic results will be reported.

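### The lowest-risk rule always names an egg exposure: the plan states no test of the average risk, no interval for its minimum and no 'no preferred level' result, and its drop-to-linear step pulls the minimum toward an end of the range

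*Combined protocol and SAP*

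**What the plan says.** The last analysis step, in 3) Project Design, Data analysis, takes predicted probabilities of stunting, underweight, obesity, high metabolic risk, food allergy and cognitive delay from the logistic models. Exposure "varies across the observed range within our study sample", the six probabilities are averaged with equal weight, and then: "We will identify the lowest-risk infant egg consumption when the corresponding average probability of the 6 adverse outcomes is the lowest". The opening summary repeats the rule: "We will identify the lowest-risk infant egg consumption when the corresponding average predicted probability of the related adverse outcomes is the lowest". A published method is cited "for identifying the lowest-risk exposure level when multiple outcomes are considered", but its content is not reproduced.

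For Aim 1, linear "and non-linear (e.g., threshold effect) associations will be tested" for each outcome, with this fallback: "If the polynomial terms of age are not significant, we will drop it and consider the association to be linear". Aim 2 is to use similar methods. After multiple imputation the plan will "pool the analytic results from all 20 imputed datasets to get the average estimates of the association", which the surrounding text ties to the specific outcome being modelled.

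Hypothesis 2 concerns the average itself: "We predict a non-linear association between age of egg introduction and the average probability of multiple child outcomes", with the optimum between 6 and 12 months. Hypothesis 3 says the same of frequency, with the optimum at 2-4 times per week.

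**The concern.** A curve over a finite range has a lowest point whether or not exposure matters. A rule that reports the lowest point, with nothing else attached, gives the same kind of answer for a flat curve as for a real trough. The reader of the result could not tell the two apart.

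The fallback to a straight line adds a second problem. It is applied outcome by outcome, before averaging. A fitted line has its minimum at an end of the range, so the fallback works against finding the interior optimum that Hypotheses 2 and 3 predict, even where one exists. It steps down to linear and never to no association.

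At stake is the plan's integrating result: one age and one frequency described as lowest-risk, without evidence that the data separate them from other levels.

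**Working it through.** **Text check.** The plan gives no power, error rate or precision for this rule, so there is no figure to reproduce. Its stated tests are chi-square/ANOVA comparisons, polynomial terms, the interaction with outcome age and the interaction with sex. All concern single outcomes. None is a condition for applying the rule, and none tests the average or the location of its minimum.

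**Why the minimum goes to an end.** If six independent outcomes are truly unrelated to exposure and each polynomial is tested at 0.05 (assumed for this step), all six fall back to lines with probability 0.95^6 = 0.735. At least one false curve is kept with probability 1 - 0.735 = 0.265. With six lines and small slopes the average is close to straight, so its minimum is usually at an end.

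**Size of the noise.** N = 2,128 is the plan's figure for Project Viva. Prevalences are assumed: stunting 2.3%, underweight 5%, obesity 5%, metabolic 5%, allergy 8%, cognitive delay 15.9%.
- Mean risk: 41.2% / 6 = 6.9%.
- SD of a child's mean of six uncorrelated outcomes: sqrt(sum of p(1-p)) / 6 = sqrt(0.3723) / 6 = 0.102.
- A group holding 30% of children (638): standard error 0.102 / sqrt(638) = 0.40 percentage points.
- A group holding 2% (about 43): 0.102 / sqrt(43) = 1.56 points.

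Chance alone can therefore move the average in a sparse group by more than a point.

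**Simulations of the rule.** Further assumptions: three sets of frequency shares (15/20/25/30/8/2, 10/20/30/30/9/1 and 20/20/20/25/10/5%), frequency scored 0-5, a quadratic standing in for the fractional polynomial and kept only if p < 0.05, obesity 5% or 12%, and latent outcome correlation 0 or 0.3. Ranges cover these settings and repeated runs.

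| Setting | Named level |
|---|---|
| Frequency, no association | an end in 68-81%; 2-4/week in under 10% (mostly 4-7%) |
| Frequency, true smooth optimum at 2-4/week, 'never' 1.75 points higher, plan's fallback | 2-4/week in about 16-27%; an end in about 52-63% |
| Same, common quadratic for all six outcomes | 2-4/week in about 38-58%; an end in about 10-21% |
| Age, no association, range ending at 12 m | an end in 70-81%; strictly inside 6-12 m in 16-23% |
| Age, no association, range 2-18 m | an end in about 68%; 6-12 m in 14% |

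In 52-56% of the frequency datasets with no association, no outcome had a significant linear or quadratic term, yet a level was still named. The median spurious spread was 0.6-1.1 points. If frequency is instead fitted as six free categories, the pull to the ends disappears and the sparsest category is lowest in 27-41%, with a median spread of 1.6-3.0 points.

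A common curve alone does not cure the flat case. With the quadratic always kept and no association (age 2-18 m), a level was still named every time, 26% of them in 6-12 months.

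**Separate check on frequency.** Project Viva first records frequency at the 2-y survey, although the Frequency of egg intake section calls it infant intake. Metabolic and cognition measures are described for Project Viva only. IFPS II records intake at 2-12 m, with a printed 12-m mean of 0.27 (SD 0.37) serving/week. The one-sided Chebyshev bound for 2 or more per week is 0.37² / (0.37² + (2 - 0.27)²) = 0.1369 / 3.1298 = 4.4%, at most about 133 of 3,033.

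**The case against.** The strongest reply is that the step is specified by reference to a published method, which may contain intervals or a test. That stands as a limit. The documents show only that none is stated, so a reader who inferred that the plan will certainly report an optimum with no measure of uncertainty would go further than the text allows.

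Second, the stated objectives are associations with separate outcomes, which are tested, and nothing says the minimum will be reported without them. That is fair, but Hypotheses 2 and 3 are about the average, and single-outcome tests do not answer them.

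Third, the percentages depend on assumed prevalences and shares, and on scoring frequency as a number. The fallback sentence names age only, and the plan classifies frequency into categories. This also stands. Only the statement that a minimum always exists is free of assumptions.

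Two stronger readings are tempting and should be resisted. A reader might infer that the rule makes Hypothesis 3 easy to confirm. It does not: with no association, 2-4/week is named in under 10% of datasets. A reader might also infer that, because most dated introductions in IFPS II fall between 6 and 12 months, a minimum there is nearly guaranteed. The share of infants in a window is not the chance that the minimum falls in it.

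On labelling, the plan openly gives the 2-y survey and the past-month recall period, and it does not promise replication of the six-outcome average in IFPS II. This is loose wording and a smaller matter.

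**Conclusion.** The concern holds as an omission that should be fixed. As stated, the rule always returns a level, with no test of the average, no interval for the minimum and no way to say that no level is preferred, while two of the three hypotheses predict the shape and minimum of that average. The harm is an unsupported named level, not false confirmation of the predicted one.

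If the fallback is carried into the averaged models (and into frequency, if scored as a number), it roughly halves the chance of naming a true interior optimum in the settings examined: about 16-27% against 38-58%. These figures are illustrative and rest on the assumptions listed above. The conclusion would narrow to one of wording if the cited method already supplies a test and an interval.

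The labelling of 2-y intake as infant intake is a real but minor and separate point.

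**What to change.** 1. Use one pre-specified form for all six outcomes when averaging: a common curve or fractional polynomial for age, and categories or a common curve for frequency. Do not drop to a line outcome by outcome.
2. Report a confidence interval for the average-risk curve and a bootstrap interval for the location of its minimum, repeating every modelling step and carried through the 20 imputations. Under no association, such a 95% location interval covered the whole frequency scale in 84-89% of simulated datasets, which shows the reader that the location is not determined.
3. Add one confounder-adjusted joint test that the average varies with exposure, for example by regressing each child's mean of the six outcomes on exposure and confounders, and a curvature test for Hypotheses 2 and 3. State that no level is preferred when the data do not distinguish levels, and that a minimum at the end of the range does not support an interior optimum. Whether to use the test as a strict gate or to report it beside the interval is partly preference.
4. State where 'never' and '>=12 m' sit on the age curve; 100 - 63.0 = 37.0% of IFPS II infants had not been introduced to eggs by 12 m.
5. If the cited method already provides items 2 or 3, say so in the plan.
6. Label the six-outcome frequency result as intake at about 2 y, Project Viva only. A first-year IFPS II analysis can cover only stunting, underweight, obesity and food allergy, and could have few infants at 2-4 times/week.

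**Cost.** Plan wording, computing time and a narrower claim; no new data. In simulations with no association, a 5-df category version of the adjusted test rejected in 3.2-5.2%, and in 3.3-4.8% after pooling 20 imputations. The 2-df version and the curvature test were not checked for error rate, and no power is available for the curvature test.

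Small real optima may go unnamed. For a 1.75-point dip in the 2-4/week group only (obesity 5%), the 5-df test has 76-81% power with uncorrelated outcomes and 56-62% at correlation 0.3; for 1 point, 28-31% and 20-22%. A 2-df quadratic has only 26-42% for that 1.75-point dip and suits a threshold poorly. For a smooth curve it has 39-72% at 1.75 points and 84-99% at 3 points. The form must therefore be chosen in advance.

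### With 20 imputations, borderline significance decisions on curve shape and on sex-stratified reporting can change with the imputation seed; raising the number is a low-cost refinement.

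*Combined protocol and SAP*

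**What the plan says.** The missing-data paragraph of Data analysis (section 3, Project Design) sets the number of imputations at 20 and gives no reason for it: "we will first generate 20 replicates of datasets (PROC MI in SAS) with imputed values for missing data on infant egg consumption". The imputation covers "imputed values for missing data on infant egg consumption, child outcomes, and significant covariates, based on a bayesian approach". The model of interest is fitted in each completed dataset and the results are pooled with PROC MIANALYZE. The plan gives no missing-data rate, random seed or check on Monte Carlo error.

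Two rules in the same section turn a significance test into a choice:

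- **Curve shape (Aim 1, and Aim 2 by similar methods):** "If the polynomial terms of age are not significant, we will drop it and consider the association to be linear". Scatter plots are also inspected, but the rule for dropping terms rests on significance.
- **Reporting by sex:** "If the interaction term is significant, sex-stratified results will be reported. Otherwise, sex-pooled analytic results will be reported".

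The logistic models then supply predicted probabilities for six adverse outcomes. These are averaged with equal weight to find the lowest-risk age or frequency.

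**The concern.** A pooled p-value from a finite number of imputations carries random error from the imputation draws. The pooled estimate moves, and so do its standard error and reference degrees of freedom. A number of imputations that is ample for the point estimate can therefore be thin for a p-value that is read against a threshold.

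In this plan such p-values select the functional form and the reporting format. Near the threshold, the same data analysed with another seed could give a straight line in place of a curve, or pooled results in place of results by sex. Hypotheses 2 and 3 concern non-linearity and the location of an optimum, so the curve-shape rule is close to the main question.

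**Working it through.** **Inputs from the plan.** m = 20 imputations; exposure, outcomes and covariates imputed; pooling with PROC MIANALYZE; two significance-based rules. The figure of 20 is a choice without a derivation, so there is no calculation in the plan to reproduce.

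**Assumptions.**
- FMI: not stated; range 0.1 to 0.7.
- Threshold: two-sided 0.05 for both rules. The plan gives 0.05 only under Statistical Power, without sidedness.
- The polynomial and interaction tests use the pooled results.

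**Method.** Hold the data fixed and call the p-value with unlimited imputations the limiting p, with corresponding z-value z. Scale the total variance to 1, so that the between-imputation variance is B = FMI and the within-imputation variance is W = 1 − FMI. For each seed:
- pooled estimate ~ N(z, B/m)
- estimated between-imputation variance B̂ ~ B·χ²(m−1)/(m−1)
- total variance T = W + (1 + 1/m)·B̂
- reference t with (m−1)(1 + 1/r)² degrees of freedom, where r = (1 + 1/m)·B̂/W

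If a share s of seeds gives p<0.05, two seeds disagree with probability 2s(1−s).

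**Seed noise in the estimate.** Its SD is √(FMI/m) standard errors. At m = 20 this is √(0.1/20) = 0.07, √(0.3/20) = 0.12, √(0.5/20) = 0.16 and √(0.7/20) = 0.19.

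**Hand check at limiting p = 0.03, FMI 0.5, m = 20.**
- z = 2.170. The mean of T is 0.5 + 1.05 × 0.5 = 1.025, so the standard error is about 1.012 and the test statistic centres on 2.170/1.012 = 2.14.
- The estimate contributes 0.158/1.012 = 0.156 to the SD of the statistic.
- The SD of T is 0.525 × √(2/19) = 0.170. This is a relative SD of 0.083 in the standard error, or 0.178 on the statistic.
- Combined SD: √(0.156² + 0.178²) = 0.237.
- With r = 1.05, the degrees of freedom are 19 × (1 + 1/1.05)² = 72, and the critical value is 1.99.
- The chance of missing significance is about Φ(−(2.143 − 1.993)/0.237) = 0.26, so disagreement is about 2 × 0.26 × 0.74 = 0.38. Simulation gives 37%.

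**Simulated disagreement between two seeds, data held fixed.**

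| Limiting p | m | FMI 0.1 | 0.2 | 0.3 | 0.5 | 0.7 |
|---|---|---|---|---|---|---|
| 0.01 | 20 | 0% | 0% | 0.1% | 2% | 9% |
| 0.03 | 20 | 1% | 11% | 22% | 37% | 45% |
| 0.04 | 20 | 23% | 38% | 44% | 49% | 50% |
| 0.20 | 20 | 0% | 0% | 0% | 0.1% | 0.9% |
| 0.03 | 100 | 0% | 0% | 0.4% | 5% | 13% |
| 0.04 | 100 | 0.8% | 8% | 18% | 32% | 40% |

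At a limiting p of exactly 0.05, disagreement is close to 50% for any m.

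**Disagreement per test, averaged over sampling variation.** Here z is itself drawn around its true value.

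| True z | m | FMI 0.1 | 0.3 | 0.5 | 0.7 |
|---|---|---|---|---|---|
| 0 | 20 | 1.1% | 2.0% | 2.9% | 3.8% |
| 0 | 100 | 0.4% | 0.9% | 1.3% | 1.7% |
| 1.96 | 20 | 3.5% | 7.2% | 10.3% | 13.4% |
| 1.96 | 100 | 1.6% | 3.1% | 4.5% | 5.8% |

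Moving from 20 to 100 imputations removes slightly more than half of the disagreement throughout.

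**The case against.** The strongest reply is that the effect is confined to tests near the threshold and depends on an FMI that the plan does not give. Both parts stand. At a limiting p of 0.01 or 0.20 the decision is almost always stable, apart from 2% and 9% disagreement at p = 0.01 with FMI 0.5 and 0.7. At FMI of about 0.2 or less, the seed noise in the estimate is at most a tenth of a standard error, and 20 imputations is a conventional choice. Low FMI does not remove the effect at the margin, however: at p = 0.04 two runs still disagree in 23% of cases at FMI 0.1. Follow-up into the teens with fasting blood and DXA gives no ground for assuming low FMI.

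A second reply is that seed noise (0.07 to 0.19 of a standard error) is small beside sampling error (1 standard error), so decisions gated on significance are fragile at any m. That also stands. A larger m reduces only the avoidable part of the fragility.

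Third, the plan does not say that the selection tests are run on the pooled results. This is inferred from its description of fitting the model of interest in each dataset and then pooling.

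A reader might go further and infer that the lowest-risk age depends on the seed. The documents do not support that. A changed decision would alter the shape of one of six averaged curves, and nothing shows that the minimum would move. Nor do they support calling 20 an error: without an FMI, the text cannot establish that it is too few.

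**Conclusion.** The point holds as an optional refinement. The plan combines an unexplained 20 imputations with two significance-gated choices, so a borderline choice can depend on the seed. The size is modest on average: about 1-4% per test under the null and 4-13% at a true z of 1.96. It is large only near the threshold, where it runs from about 1% to 45% at a limiting p of 0.03. These figures rest on an assumed FMI of 0.1 to 0.7, a two-sided 0.05 threshold, and selection tests run on pooled results. The rules apply across several outcomes and both aims, so the number of tests exposed is greater than one. I give no combined figure because the dependence between the tests is unknown.

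**What to change.** In the missing-data paragraph, change the number of imputed datasets from 20 to at least 100 and state the seed in advance. State that the polynomial and sex-interaction tests use the pooled results, and report the Monte Carlo error of their p-values. Where that error spans 0.05 at the final number of imputations, report both versions: linear and non-linear, or sex-pooled and sex-stratified. This gives a stopping point, which repeatedly raising m would not: at m = 100 and a limiting p of 0.04, two seeds still disagree in 18% to 40% of cases for FMI 0.3 to 0.7. The stated seed makes a rerun identical but does not make a borderline choice less arbitrary, so it does not replace the other steps.

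The cost is one number and a few sentences, plus computing time for 2,128 + 3,033 = 5,161 children. No new data are needed. The change is best made before analysis, so that neither the seed nor the number of imputations can appear to have been chosen after seeing results.

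### The imputation model is not made compatible with the curvature and egg-by-sex tests it feeds; entered as main effects only, it would shrink both effects

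*Combined protocol and SAP*

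**What the plan says.** The missing-data paragraph of Data analysis (combined protocol and SAP, Project Design) gives three stages. The first reads: "we will first generate 20 replicates of datasets (PROC MI in SAS) with imputed values for missing data on infant egg consumption". The list of imputed variables continues with "child outcomes, and significant covariates, based on a bayesian approach". The second stage fits the analysis model in each dataset, and the third pools the results with PROC MIANALYZE.

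Nothing more is specified. The plan does not give the predictors in the imputation model or the PROC MI method. It does not say whether polynomial or product terms are included, or whether imputation is done by sex. It gives no missing fraction or mechanism and plans no complete-case comparison.

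The models that use the imputed data are more specific:

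- Aim 1 fits "regression models with fractional polynomial functions of infant age of egg introduction" and judges non-linearity by plots and by "statistical tests of polynomial term of infant age of egg introduction in the regression models". The rule is: "If the polynomial terms of age are not significant, we will drop it and consider the association to be linear". Aim 2 applies similar methods to frequency of intake.
- The sex difference is tested by "including the interaction term of egg consumption and sex into the regression models". The result decides whether stratified or pooled estimates are reported.
- Hypothesis 2 reads: "We predict a non-linear association between age of egg introduction and the average probability of multiple child outcomes". Hypothesis 3 is its counterpart for frequency.

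**The concern.** An imputed value can carry only the relations that its imputation model contains. If exposure, outcome and sex enter as main effects, an imputed exposure is related to the outcome along a straight line with the same slope in boys and girls. Those records then dilute the curvature and the interaction seen in the observed records. The same happens when the outcome is imputed from a main-effects model.

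The two diluted quantities are the plan's own decision tests. A weakened polynomial term is dropped and the association reported as linear. A weakened interaction leads to pooled reporting. The lowest-risk age and frequency are read from predicted probabilities of the same logistic models, so flattened curves can also move that result.

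**Working it through.** **The plan's own figures.** There is none for missing data. The Statistical Power section gives detectable odds ratios of 1.46 (N=2,128) and 1.38 (N=3,033) at 0.05 and 80% power. With an assumed 10% base rate and 1:1 split, a two-sided comparison of proportions gives 80.3% and 80.8%. The odds ratios are therefore consistent with full cohort sizes and say nothing about missing data.

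**Expected size.** If a share p of exposures is imputed without the term, the pooled coefficient is roughly (1 − p) × truth + p × 0, a ratio of 1 − p.

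**Simulation.** From the plan: N=2,128, 20 imputations, pooling across imputed datasets. Assumed: a continuous outcome with residual SD 1, coefficient 0.05 on squared exposure and 0.13 on exposure × sex, one covariate, and exposure missing completely at random. There were 400 runs, and the error on power is about 2 to 4 points. Ratios are estimate/truth:

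| Exposure missing | 1 − p | Curvature, main-effects imputation | Interaction, main-effects imputation |
|---|---|---|---|
| 10% | 0.90 | 0.90 | 0.93 |
| 30% | 0.70 | 0.71 | 0.75 |
| 50% | 0.50 | 0.50 | 0.56 |

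Complete-case ratios were 0.99 to 1.04.

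Methods compared at 30% missing:

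| Method | Curvature: ratio, power | Interaction: ratio, power |
|---|---|---|
| Complete cases | 1.00, 79% | 1.03, 74% |
| Main-effects imputation | 0.71, 52% | 0.75, 53% |
| Main-effects imputation, by sex | 0.70 (power not tabulated) | 1.03, 75% |
| Imputation compatible with the analysis model | 0.99, 78% | 1.01, 72% |

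**In terms of the plan's rules.** A truly curved association would be called linear in 100 − 52 = 48% of studies, against 100 − 79 = 21% with complete cases. A real sex difference would be pooled away in 100 − 53 = 47%, against 100 − 74 = 26%.

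**Variations.**

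- Binary outcome, 30% of exposure missing (250 runs): curvature 0.72 and 0.71, interaction 0.77 and 0.80, at N=2,128 and 3,033. Complete cases gave 0.95 to 1.05.
- Missingness strongly dependent on the outcome, 30%: main-effects imputation 0.61 and 0.66, complete cases 0.85 and 0.88, compatible imputation 0.97 and 1.00 (curvature, interaction).
- Outcome 30% missing, exposure complete (300 runs): 0.73 and 0.72. Power was 56% against 81% with complete cases for curvature, and 45% against 72% for the interaction.
- Exposure 20% and outcome 30% missing: the share with both observed is 0.8 × 0.7 = 0.56, and the ratios were 0.57 and 0.58. Power was 25% against 69%, and 22% against 63%.
- Logistic outcome, polynomial term carried as one more variable in the imputation, about 30% of exposure missing (150 runs): curvature was 1.10 of truth when missing completely at random and 1.30 when missingness depended on outcome and covariate. Complete cases gave 1.00 in both. This shortcut overshoots.

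**The case against.** The strongest reply is that the plan never says these terms are left out. It says only "based on a bayesian approach", and a careful analyst could include them. That is correct: the documents show an unspecified model, not a wrong one. The point still needs action, because entering the named variables into PROC MI with no added terms fits the text as written and produces the attenuation above.

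Second, Data analysis says twice that all analyses are first run in boys and girls separately. If imputation follows that split, the interaction is preserved. This stands, but the plan does not say that it does, and the split leaves curvature at 0.70.

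Third, a reader might infer that the planned imputation is worse than none. The documents do not support that as a general statement. With only exposure missing, it held for bias and power in every scenario run, but not always for root mean squared error: at 10% missing, imputation had the lower error for both terms (0.0160 against 0.0168; 0.0427 against 0.0455). The plan also imputes covariates and lists many confounders. With 10% missing on exposure and on each of five covariates, only 0.9^6 = 53% of records are complete. Main-effects imputation then beat complete cases on power (79% against 71% for curvature, 73% against 61% for the interaction) and on root mean squared error.

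Fourth, a reader might take the phrase about significant covariates to restrict the predictors and so drop causes of missingness. The sentence names what is imputed; it does not say which variables may predict.

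Finally, the simulations use a continuous exposure and a quadratic term. The plan has a group never fed eggs, fractional polynomials and ordered frequency classes. The sizes are therefore illustrative.

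**Conclusion.** The concern holds in conditional form. The plan imputes exposure and outcomes without tying the imputation model to the polynomial and egg-by-sex terms on which it bases decisions. Under a main-effects imputation both effects shrink roughly with the share imputed, to about 0.9 of truth at 10% and about 0.7 at 30%. The loss was larger when missingness depended strongly on the outcome, or when exposure and outcome were both incomplete. The direction follows from the method. The size rests on assumed missing rates, effect sizes and mechanisms, because the documents state none. This should be changed before analysis. It is not a reason to abandon imputation, since a compatible model removes nearly all of the bias in these runs.

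**What to change.** Specify the imputation model in the missing-data paragraph:

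- Impute boys and girls separately.
- Impute exposure and outcomes with a method compatible with the analysis model, such as substantive-model-compatible fully conditional specification, holding the polynomial terms that the analysis may test. For the logistic outcomes, do not simply carry the polynomial terms as extra variables.
- Enter repeated outcomes in wide format, so that each visit can have its own relation to exposure.
- Use all listed confounders as predictors, whether or not they are significant in the analysis model.
- Report the missing fraction for exposure, each outcome and each covariate, by cohort.
- Add a complete-case sensitivity analysis for the curvature and interaction tests.

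The cost is SAP wording, some programming (a compatible method is tied to a given analysis model, so it is run for each one) and computing time. No new data are needed.
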